Official Title of the study: Antimicrobial Efficacy of Xylitol, Probiotic and Chlorhexidine Mouth Rinses Among Children and Elderly Population at High Risk for Dental Caries - A Double Blind Randomized Controlled Trial.

NCT ID: NCT04399161

Date: 22-05-2020

Study Protocol

Need for the study:

World Health Organization defines dental caries as a localized, post eruptive pathological process of extreme origin involving softening of the hard tooth tissue and proceeding to the formation of cavity. The process involves bacterial interactions in plaque accumulated on the surface of the teeth. *Streptococcus mutans* in plaque is the most commonly isolated organism amidst all other cariogens. It ferments sucrose and the resulting acid causes demineralization of tooth enamel.

While mechanical methods of plaque control can maintain adequate oral hygiene, such methods are not being utilized appropriately by the population. This necessitates use of adjuncts to mechanical plaque control methods in the form of antiplaque mouth rinses. Chlorhexidine mouth rinse has been considered the most effective agent in inhibiting *Streptococcus mutans*. Although considered the gold standard, its adverse effects due to prolonged use such as staining of teeth, xerostomia, altered taste sensation, mouth/ throat irritation, antimicrobial resistance, etc. indicates the need for alternatives which have been extensively studied of late in literature.

Xylitol used as an artificial sweetener in foods, is a non-cariogenic sugar substitute. This polyalcohol cannot be metabolized by oral bacteria thereby preventing caries. The magnitude of adverse effects caused by xylitol as compared to that of Chlorhexidine is indistinct. Although studies have assessed effects of xylitol chewing gum on caries, very few have studied its efficacy as a mouth rinse.

Probiotics are live microorganisms that, when administered in adequate amounts, confer a health benefit on the host. Probiotic products seem to have an effect on the oral health of individuals by prompting beneficial bacteria to defend teeth and gums against harmful ones.

The advantages of probiotics as compared to that of chlorhexidine mouth rinse are that there are no issues of antibiotic resistance as it contains only commensal flora and there has been no proof of intoxication or allergies on consumption.

Antimicrobial efficacies of probiotics and xylitol mouth rinses have not been compared till date. Also their effects on the young and elderly population have not been compared. Hence the purpose of the present study is to compare the antimicrobial efficacies of probiotic and xylitol mouth rinses with the gold standard in children and elderly population.

Aim of the study:

To compare the antimicrobial efficacy of probiotic and xylitol mouth rinses with chlorhexidine (gold standard) among children and elderly population at high risk for dental caries.

Objectives of the study:

1. To assess *Streptococcus mutans* levels at baseline and 14 days after intervention in children and elderly population.
2. To compare efficacies of the 3 mouth rinses in reducing *Streptococcus mutans* levels in children and elderly.

Materials and methods:

Source of data: Residential school children aged 5-12 years at high risk for caries. Elderly population above 60 years residing in old age homes at high risk for caries.

Eligibility Criteria:

Inclusion Criteria:

1. Children aged 5-12 years at high risk for caries.
2. Elderly citizens (above 60 years) at high risk for caries.
3. Those willing to participate in the study and consented.
4. Not under antimicrobial therapy or used probiotic products during past 1 month.

Exclusion Criteria:

1. Using mouth rinse routinely.
2. Undergoing any dental treatment during the study period.
3. Not able to brush their teeth and rinse on their own.

Study Design: Double Blind Randomized Controlled Trial.

Sample Size: Twelve participants will be chosen per group. With 3 products involved in each of the 2 population groups (children and elderly) the sample size will be 36 child participants and 36 elderly participants.

Consent from participants: Permission to conduct the study in the residential school and old age home will be obtained from the concerned authorities. Details about the study will be presented to the participants in the form of a study information sheet or communicated verbally in both English and in the local language. Only the eligible participants who provide written

consent will be included in the study. In case of children, written consent will be obtained from the guardians.

Caries risk assessment: Individuals with high caries risk will be identified using a customized caries risk assessment tool. The caries risk assessment tool will comprise of information on socio economic status, oral hygiene practices, fluoride exposure, caries experience amongst family members, symptoms of dry mouth, quantity and frequency of intake of sweetened food and caries experience in the past and present. Each item will be scored as 0 or 1 and the total score will be obtained by summing up the scores of all the items. Any participant with total score greater than 5 will be considered to be at high risk for caries.

Method:

1. Preparation of mouth rinses
2. Baseline data collection and Microbial Analysis
3. Randomization and Group Allocation
4. Intervention
5. Post intervention data collection and Microbial Analysis

1. Preparation of mouth rinses:

Xylitol mouth rinse at 10 percentage concentration will be used. Probiotic mouth rinse will be prepared by using a commercially available probiotic product (Sporolac Plus powder- 1gm sachet containing not less than 1.5 billion cells of *Lactobacillus acidophilus*, *Lactobacillus rhamnosus*, *Bifidobacterium longum*, *Bacillus coagulans* and *Saccharomyces boulardii*). Each

sachet will be dissolved in 15 ml of water in a measuring cup and will be used as a mouth rinse. A commercially available Chlorhexidine mouth rinse (Hexidine- 0.2 percentage Chlorhexidine gluconate) containing 0.2 percentage chlorhexidine gluconate per 10 ml will be used.

2. Baseline data collection and microbial analysis:

Plaque samples will be collected from the buccal surface of a non-carious permanent maxillary first molar. Plaque collection will be done using an autoclaved scaler under daylight. The collected plaque will be stored in a pre-weighed sterile eppendorf tube. Tubes will be weighed again after plaque collection. The weight of the collected plaque (in grams) will be determined by subtracting the weight of the empty eppendorf tube from the weight of the tube with the collected plaque. The samples will be stored at - 4 degree Celsius and transported to a culture lab within an hour to avoid using transport media.

1 ml saline will be added to the eppendorf tube and vortexed for even distribution of plaque. This mixture will be used as stock solution for serial dilutions. From the stock solution, 100 μ l will be transferred to a sterile test tube containing 900 μ l of saline and vortexed to arrive at 1:10 dilution. Similar dilutions will be prepared to obtain 1/10, 1/100 and 1/1000 dilutions. 50 μ l from each of the dilutions will be plated onto the selective medium MSB (Mitis Salivarius Bacitracin Agar) by spread plate method. After plating, the MSB (Mitis Salivarius Bacitracin Agar) agar plates will be placed in the anaerobic jar and incubated at 37 degree Celsius for 72 hours.

Colonies of *Streptococcus mutans* will be identified based on the following morphologic characteristics, a) 0.5 mm raised convex undulated colonies b) light blue colour with rough margins c) granular frosted glass appearance. The colonies will be confirmed by a catalase test (negative catalase reaction) and gram staining (gram positive cocci). Bacterial colonies will be counted manually. The standard formula for determining Colony Forming Units (CFU) will be $CFU/g = [Number\ of\ colonies \times Dilution\ factor] / [Volume\ plated\ (in\ ml) \times Amount\ of\ plaque\ (in\ g)]$

3. Randomization and Group allocation: After data collection at baseline, the study participants will be allocated to three groups, Group A, B and C, by simple random sampling (lottery method). Group A will be given Chlorhexidine mouth rinse; Group B will be given Xylitol mouth rinse and Group C Probiotic mouth rinse. The participants and the investigator will be blinded from the allocation sequence.

4. Intervention: The participants will be asked to rinse their mouth once daily (at night) for 2 minutes, using 15 ml of mouth rinse. The intervention will be carried out for a period of 14 days. Mouth rinsing will be supervised during the study period by an assistant. A record will be maintained to document regular usage of the mouth rinse and also to record any adverse effects occurring during the intervention period.

5. Post intervention data collection: After 14 days of using the mouth rinses, the same procedures will be repeated and compared with baseline.

Statistical Analysis Plan: Data will be analysed using SPSS (Statistical Package for the Social Sciences Version 22.0; SPSS Incorporated, Chicago, Illinois). Comparisons before and after interventions will be done using Paired t Test. Comparisons between Chlorhexidine, probiotic and xylitol groups will be done using ANOVA (Analysis of Variance) and Tukey's Post Hoc Tests. Comparison of antimicrobial efficacy of mouth rinses between children and elderly will be done using Independent sample t Test. Statistical significance will be fixed at $p \leq 0.05$.

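### No entry rule requires countable S. mutans at baseline and nothing stronger than a 1/10 dilution is plated, so some participants cannot show the reduction under study and low day-14 counts are poorly measured

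*Combined protocol and SAP*

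**What the plan says.** The second objective is "To compare efficacies of the 3 mouth rinses in reducing" S. mutans levels; the first is to assess those "levels at baseline and 14 days after intervention in children and elderly population".

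Entry is defined by caries risk. Source of data names "children aged 5-12 years at high risk for caries", and inclusion criterion 2 reads "Elderly citizens (above 60 years) at high risk for caries". Under Caries risk assessment, risk is a sum of 0/1 items: "information on socio economic status, oral hygiene practices, fluoride exposure, caries experience amongst family members, symptoms of dry mouth", then sweet intake and past and present caries. The cut-off is "Any participant with total score greater than 5 will be considered to be at high risk for caries". No item and no inclusion or exclusion criterion refers to S. mutans.

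Under Method, item 2, the plaque is suspended in 1 ml of saline as a stock, and the stock is described only as the source for dilution: "Similar dilutions will be prepared to obtain 1/10, 1/100 and 1/1000 dilutions". From each dilution 50 microlitres are plated; plating of the stock itself is not listed. The result is expressed as CFU per gram of plaque.

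Item 3 places the lottery after sampling: "After data collection at baseline, the study participants will be allocated to three groups". No step uses the culture result. The Statistical Analysis Plan names t tests, ANOVA and Tukey comparisons, with no transformation, detection limit or rule for zero counts.

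**The concern.** A person whose baseline plate is empty has nothing measurable to lose. Whichever rinse is allotted, the recorded change cannot be a reduction, so that person carries no information for objective 2 and pulls the arm means together. With 12 per group there is little room for such people.

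The dilution scheme adds to this at day 14. All three plates are placed towards high counts, while the trial looks for falls. A successful rinse moves samples into the range where the 1/10 plate shows one colony or none, and there the count says little about how far the level fell. The limit is expressed per gram, so it rises if less plaque is collected at the second visit. The plan does not say how such samples are scored, and the answer can change the estimated difference between rinses.

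**Working it through.** **Inputs from the documents.** 1 ml stock; first dilution 100/(100 + 900) = 1/10; 0.05 ml plated; CFU/g = colonies x dilution factor / (ml plated x g plaque); 12 per group, 12 x 3 x 2 = 72 people. No effect size, SD or power is stated, so there is no planned figure to reproduce beyond that product.

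**Inputs not in the documents, assumed.** Plaque weight w (1 to 10 mg), baseline load, and the share p of true non-carriers.

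**1. Floor.** One colony on the 1/10 plate is 1 x 10/(0.05 x w) = 200/w CFU/g. On undiluted stock it would be 1 x 1/(0.05 x w) = 20/w.

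| Plaque (assumed) | Floor at 1/10 | Floor with stock plated |
|---|---|---|
| 1 mg | 200,000 | 20,000 |
| 2 mg | 100,000 | 10,000 |
| 5 mg | 40,000 | 4,000 |
| 10 mg | 20,000 | 2,000 |

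**2. Chance of an empty plate.** Expected colonies = CFU/g x w x 0.05/10, and P(0) = exp(-expected). At 2 mg:
- True 10^5 CFU/g: 10^5 x 0.002 x 0.005 = 1 colony, P(0) = 37%. On stock: 10 colonies, P(0) below 0.01%.
- True 10^4 CFU/g: 0.1 colony, P(0) = 90%. On stock: 1 colony, P(0) = 37%.

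**3. Raw CFU/g.** At 2 mg each colony scores 100,000. For a true 10^5 the mean recorded value is 1 x 100,000 = 100,000 despite 37% zeros; for a true 10^4 it is 0.1 x 100,000 = 10,000 despite 90% zeros. The mean is unbiased and the single reading is noisy.

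**4. Log10.** Simulation with 12 per arm, true reductions of 2 and 1 log10 (true difference 1.0), 2 mg, baseline mean 10^6 CFU/g, baseline SD 0.8 and change SD 0.5, all assumed:
- zeros set to the floor: observed difference 0.30;
- log10(CFU+1): observed difference about 2.0.

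The gap arises because one empty plate scores log10(100,000) = 5 under the first rule and 0 under the second. Adding the stock plate raised power from about 22% to 82% under the first rule and from about 47% to 70% under the second.

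**5. Dependence on load, zeros set to the floor.** With the same reductions and SDs, the observed difference is 0.20 at a mean of 10^3 viable cells per tube, 0.57 at 10^4, 0.89 at 10^5 and 0.99 at 10^6. At 2 mg, 10^6 CFU/g is 10^6 x 0.002 = 2 x 10^3 cells, near the bad end; 10^8 CFU/g is 2 x 10^5 cells, so the difference lies between 0.89 and 0.99. At 10^4 cells the stock plate moves 0.57 to 0.89 and power from 64% to 98%.

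**6. Non-carriers.** Their change is zero on every rinse, so the mean difference becomes (1-p) times the true one. A difference of 0.5 log10 becomes 0.45, 0.40 or 0.35 at p = 10%, 20% or 30%. The chance of at least one in a group of 12 is 1 - (1-p)^12: 72% at 10%, 93% at 20%. In the simulation at 10^6 cells per tube, where the floor hardly matters, p = 20% lowers the difference from 0.99 to 0.79 and power from 99% to 64%.

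**The case against.** Enrolling on caries risk is what the title and aim announce, so the score is not itself a fault. A score above 5 on about seven listed domains, including sweet intake and caries experience, may select people who nearly all carry S. mutans, which the protocol calls the most commonly isolated cariogen. The 1/1000 plate suggests that high loads were expected: at 2 mg one colony there is 1 x 1000/(0.05 x 0.002) = 10^7 CFU/g. And CFU/g is the only scale the plan names, on which step 3 shows no bias in the mean. All of this stands. It limits the size of the problem, but the documents give no load, plaque weight or carriage figure that places the samples in the safe range, and an empty baseline is uninformative on any scale.

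A reader might go further and infer three things that do not hold:
- *That everything below the floor is recorded as zero.* At 2 mg a true 10^4 CFU/g gives a non-zero plate about 10% of the time.
- *That the result is always biased towards no difference, favouring the alternatives to chlorhexidine.* On raw CFU/g low counts leave the mean unbiased; on log10 the direction depends on the zero rule. The plan also claims neither non-inferiority nor equivalence. From 10^6, ten-fold and hundred-fold falls are raw changes of 900,000 and 990,000; they look alike because of the scale, and a stronger plate would not alter that.
- *That 12 per arm is worth only 10 to 6.* This is 12(1-p)^2 = 9.7 to 5.9 for p = 10% to 30% at an unchanged SD. It illustrates an assumed p and is not a finding about this trial.

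**Conclusion.** The point holds as a gap in design and measurement, without a demonstrated direction of bias. Three facts rest on the text alone: no entry rule concerns S. mutans, the lottery does not use the baseline culture, and the one-colony floor is 200/w CFU/g. It follows that people with empty baseline plates can be randomised and cannot show a reduction, and that true non-carriers shrink the mean difference by (1-p).

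The size is conditional. At an assumed 2 mg, on log10 with zeros set to the floor, the loss is large near 10^6 CFU/g (1.0 read as 0.30) and small near 10^8; with log10(CFU+1) at 10^6 the difference is exaggerated to about 2.0. On raw CFU/g the cost of low counts is noise. Since load, plaque weight and p are unstated, the case for change rests on the low cost of the remedy more than on proven harm.

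**What to change.** 1. **Method, item 2, and Statistical Analysis Plan.** At baseline and day 14, also plate 50 microlitres of the undiluted stock. This lowers the floor tenfold; where the stock plate is too crowded to count, the dilutions remain. Record a zero as below that sample's floor, with the floor computed from its plaque weight. Name the analysis scale and one pre-specified rule for such values.
2. **Eligibility Criteria and Method, item 3.** Require countable S. mutans on the baseline culture, run the lottery after the 72-hour read, and replace people without countable S. mutans before allocation. The extra plate alone cannot help with true non-carriers.

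**Cost.** 72 x 2 = 144 extra plates, about three days between baseline sampling and the lottery, and a few more people screened. Results would apply to high-risk carriers, a narrower population than the stated aim. Selecting on a noisy baseline count also brings some regression to the mean into the paired before-after tests; the randomised comparison between rinses is not biased by it.

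### Does the plan need changing because no eligibility criterion requires the sampled molar and day 14 is not explicitly tied to the same tooth?

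*Combined protocol and SAP*

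**What the plan says.** Method 2 (Baseline data collection and microbial analysis) fixes the sampling site: "Plaque samples will be collected from the buccal surface of a non-carious permanent maxillary first molar". The CFU/g value is computed from that sample, and S. mutans level is the only efficacy measure in the Objectives.

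The Source of data and Eligibility Criteria sections define the populations as residential school "children aged 5-12 years at high risk for caries" and "Elderly citizens (above 60 years) at high risk for caries". The other criteria cover consent, recent antimicrobial or probiotic use, routine rinse use and two further exclusions: "Undergoing any dental treatment during the study period" and "Not able to brush their teeth and rinse on their own". None mentions a particular tooth.

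Under Caries risk assessment, the items scored 0 or 1 include "caries experience in the past and present", and the cut-off is: "Any participant with total score greater than 5 will be considered to be at high risk for caries".

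Method 3 sets the order of events: "After data collection at baseline, the study participants will be allocated to three groups". Method 5 has the baseline procedures repeated after 14 days and compared with baseline. The Statistical Analysis Plan uses a paired t test within groups, ANOVA with Tukey's test between rinses, and an independent-sample t test between children and elderly. It does not say whether the last two use change or day-14 levels.

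**The concern.** A person can meet every written criterion and still lack a sound permanent upper first molar. The youngest children may not yet have one, older residents may have lost theirs, and a score that rewards caries experience leans towards people whose molars are affected. The protocol does not say whether such a person is left out, sampled elsewhere, or allocated without a baseline value. If people are left out, the population studied is narrower than the one described, perhaps to a different degree in children and elderly, who are compared directly.

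The second worry is precision. Method 2 asks for one such molar without naming a side, and nothing says that the side is recorded. Sampling the left molar at baseline and the right on day 14 would add left-right variation to the change that the paired t test examines. With 12 per group there is little precision to spare.

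**Working it through.** **Planned size.** 12 per group × 3 rinses = 36 per population; 36 × 2 = 72. This reproduces the Sample Size section.

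**Timing.** Methods 2 and 3 put plaque collection before the lottery. A person without a usable molar is therefore identified before a rinse is assigned, so the tooth requirement cannot act differently across rinses. Method 3 also blinds the investigator, so the side chosen on day 14 should not depend on the rinse.

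**Caries score against a sound tooth.** Counting sweet-food quantity and frequency as one item, and past and present caries as one item, gives seven items: socioeconomic status, oral hygiene, fluoride, family caries, dry mouth, sweet foods, caries experience. Splitting both pairs gives nine. Leaving out caries experience altogether, 6 of 7 or 7 of 9 points can still be reached, and both exceed 5. The score describes the person, while the sampling rule describes one tooth. The two are compatible, and the score creates at most a tendency.

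**Screening.** Let f be the share of otherwise eligible people with neither upper first molar usable (assumed 5% to 30%). The number to screen per population is 36/(1 − f):
- f = 5%: 36/0.95 = 37.9, so 38
- f = 30%: 36/0.70 = 51.4, so 52

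If people without the tooth are not enrolled, this burden comes from the sampling site. It is the same whether or not the criterion is written.

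**Noise in change.** If the same tooth is used at both visits, the added variance is zero. Otherwise, assume that the side is picked at random at each visit, that molars are lost independently, and that the left-right to visit-to-visit variance ratio r is 0.1 to 0.5. Then:
- loss per tooth: q = √f
- share with both molars among those with at least one: (1 − q)²/(1 − f)
- share switching side: s = half of that
- variance of change relative to same-tooth sampling: 1 + s·r

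| Case | Share with both | s | Variance ratio (r = 0.1 to 0.5) | 12 acts like |
|---|---|---|---|---|
| f = 5% | 0.634 | 0.317 | 1.032 to 1.159 | 11.6 to 10.4 |
| f = 30% | 0.292 | 0.146 | 1.015 to 1.073 | 11.8 to 11.2 |
| Everyone has both | 1 | 0.5 | 1.05 to 1.25 | 11.4 to 9.6 |

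For a paired t test with n = 12 and two-sided 0.05 (the plan does not state sidedness), a standardized change of 0.89 has 80% power with the same tooth. Power is about 79% to 74% over the first two rows and 71% at the extreme of the third. An ANOVA of day-14 levels uses one tooth per person, so switching sides does not affect it.

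**The case for a change.** The case for a change is that the omissions are plain on the page, the remedy is one criterion, one sentence and one form field, and a small trial should not give away precision. It is true that the text leaves the handling of a person without the tooth undefined, and that it does not literally require the same tooth on day 14. Noting both would make the report clearer.

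Larger consequences can be calculated, but they depend on assumptions that the plan does not support. If 40% of enrolled participants could not be sampled, 12 per group would fall to 12 × 0.6 = 7.2, and power at a standardized difference of 1.20 would fall from 80% to about 56%. That requires the losses to occur after allocation, whereas baseline sampling comes first.

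Similarly, a drop in the baseline to day-14 correlation from 0.8 to 0.6 doubles the variance of change, since (1 − 0.6)/(1 − 0.8) = 2. In the terms used above, doubling needs s·r = 1. That means r of about 3.2 when s = 0.317, or r = 2 when everyone has both molars and sides are picked at random. Nothing in the documents points to left-right variation of that size.

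The population argument holds only as a matter of description. The restriction is already stated under Method 2, and moving it to the eligibility list would not alter who is studied or what the child-elderly t test compares. It is also an inference that people without the tooth are dropped; an improvised site is equally possible on the text.

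Same-tooth sampling is not entirely free of questions either, because it returns to a surface scraped 14 days earlier. The documents do not show whether that matters.

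**Conclusion.** No change to the plan follows. The gap is one of missing detail. The tooth requirement is visible in the sampling method, it takes effect before randomization, and it leaves the comparison between rinses unbiased. Repeating the baseline procedures after 14 days most naturally means returning to the same molar, and the exclusion of dental treatment during the study means that tooth should normally still be there.

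On that reading the loss is zero. On the less natural reading of random side choice, the first two assumed cases give a 1.5% to 16% rise in the variance of change, confined to analyses that use change. The 25% figure needs two usable molars in everyone and the highest assumed variance ratio, so it is the top of a chosen range and not a bound. The share without a usable molar, independent loss, random side choice and the variance ratio are all assumptions. What is firm is the wording of the plan and the order of sampling and allocation, and these are enough to settle the point.

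### Plaque for a viable count is to be held at a written temperature below zero, unexplained and with no suspending fluid or recovery check: a minor handling point that one confirmed figure would settle

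*Combined protocol and SAP*

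**What the plan says.** Under Method, step 2 (baseline data collection and microbial analysis), plaque is scraped from a molar and "The collected plaque will be stored in a pre-weighed sterile eppendorf tube". The tube is weighed again to give the plaque mass by difference. The next instruction is: "The samples will be stored at - 4 degree Celsius and transported to a culture lab within an hour", the stated purpose being to do without a transport medium.

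Fluid first appears after this, at the start of the dilution series: "1 ml saline will be added to the eppendorf tube and vortexed for even distribution of plaque". The diluted sample is spread on selective agar and incubated, and "Bacterial colonies will be counted manually". The result is expressed as CFU per gram of plaque. At day 14, under step 5, "the same procedures will be repeated and compared with baseline".

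The protocol gives no reason for the temperature. It mentions no cryoprotectant, thaw step or recovery control. The one-hour limit applies to transport; no limit is set on the time from sampling, or from arrival, to plating.

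**The concern.** A colony count registers only cells still alive when they are plated. The protocol recognises this, because it limits transport to an hour in place of a transport medium. A hold below zero without a protective medium pulls the other way, since it may kill some of the cells that the time limit is meant to preserve.

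Two things would be at stake. If the same share is lost from every sample, all counts are too low. If the share varies from sample to sample, the variation enters the change from baseline as noise, in a trial where "Twelve participants will be chosen per group". The open interval between arrival and plating leaves room for such variation.

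**Working it through.** **The plan's own figures.** The Sample Size paragraph gives 12 per group and 3 products: 12 × 3 = 36 per population, which agrees with the text, and 72 in all. No effect size, SD or power is stated, so the 12 cannot be derived. No survival figure is given either. Everything below is a sensitivity range on assumed inputs.

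**Assumptions.** The surviving share is log-uniform between s and 1, and independent between samples and between a participant's two visits. The SD of the log10 change without handling noise is 1.0. The SAP mentions no log transformation, so these figures describe a log10 change score and not necessarily the analysis that will be run.

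**Noise from variable survival.** The SD of log10 survival is −log10(s)/√12. A change score carries two samples, so multiply by √2.

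| Survival range | SD per sample | SD added to change | Added variance vs 1.0² | SE ratio |
|---|---|---|---|---|
| 50–100% | 0.301/3.464 = 0.087 | 0.123 | 0.123² = 1.5% | √1.015 = 1.008 |
| 10–100% | 1.000/3.464 = 0.289 | 0.408 | 0.408² = 16.7% | √1.167 = 1.080 |

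In terms of sample size, 12 per group would carry the information of 12/1.015 = 11.8 or 12/1.167 = 10.3.

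**Dependence on the assumed SD.** Take the difference that 12 per group would detect with 80% power in one pairwise comparison. By normal approximation, two-sided 0.05 and without Tukey adjustment, this is (1.960 + 0.842) × √(2/12) = 1.144 SD. With the added noise, power becomes:

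| Change SD (log10) | Survival 50–100% | Survival 10–100% |
|---|---|---|
| 1.0 | 79.4% | 73.7% |
| 0.5 | 77.7% | 58.3% |

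The largest loss needs both a small SD and survival falling as low as 10%.

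**Constant loss.** If every sample keeps the same share, the loss cancels in a log10 change. It does not cancel in raw CFU/g: at 50% survival, a fall from 1,000,000 to 200,000 is seen as 500,000 to 100,000, a drop of 400,000 where the true drop is 800,000. The SD shrinks by the same factor, so t and F statistics are unchanged by the scaling itself; it is the reported size of the drop that is wrong.

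**The case against.** The strongest reply is that the minus sign may not be meant. It is typed as a hyphen, a space and the digit, and the paragraph on preparing the rinses uses a hyphen and space as a dash before figures. A typing slip is plausible. This stands as a reason to ask before asserting an error, but it does not remove the point: nothing else in the protocol gives another temperature, and a slip needs the same correction.

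The second reply is that the harm is not documented. No plaque mass, container, cooling rate or total storage time is given, so whether the plaque freezes at all within the hour, and how many cells would die, cannot be read from the text. This also stands, and the loss may be small.

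Two stronger readings are tempting:

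- A reader might infer that the plaque is dried. The protocol describes no drying; the order of steps shows only that no suspending fluid is mentioned before the laboratory stage.
- A reader might infer that part of the rinse effect is produced in the tube, because cells damaged by a rinse might survive the cold less well. That would need survival to differ by arm or visit. For illustration, 90% survival at baseline and 50% at day 14 would add a false drop of log10(0.9/0.5) = 0.26. The documents show no such difference: baseline samples precede allocation, and handling is the same in every arm and at both visits.

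**Conclusion.** The concern holds as a minor measurement point. Followed literally, the protocol puts every sample through an unexplained sub-zero hold that conflicts with the evident purpose of its own one-hour limit, and the outcome is a viable count. The likely consequences are lower counts and some added noise. With an assumed change SD of 1.0 log10 and independent log-uniform survival, the noise is about 1.5% to 17% extra variance, or about 1% to 8% on the standard error. The survival ranges, the independence between visits and the SD are all assumptions, and a smaller SD would make the proportional effect larger. The documents do not establish that the samples freeze, that any particular share is lost, or that any comparison between rinses is biased.

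**What to change.** Ask the sponsor to confirm the intended storage temperature, and correct the text to an unfrozen cold hold (for example +4 degrees Celsius) at both visits. Keep the one-hour limit.

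Two additions are optional: logging the time from sampling to plating, and adding the saline before transport if the tube can be weighed on site first.

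The cost is one corrected figure, a note to staff and possibly a cool box. No change to the sample size or the analysis follows from this point.
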